2. SYNOPSIS

Name of Sponsor/Company: Eagle Pharmaceuticals, Inc.	
Name of Finished Product: Ryanodex® (EGL-4104) (dantrolene sodium) for injectable suspension)	
Name of Active Ingredient: Dantrolene sodium	
Protocol: EGL-4104-C-1801	
Title of the Study: Phase 3, Multi-Center, Double-Blind, Randomized, 2-Arm, Parallel Study to Assess the Efficacy and Safety of Ryanodex® (EGL-4104) as Adjuvant Treatment in Subjects with Exertional Heat Stroke (EHS)	
Investigator: [name], MHPE	
Study Center: Four (4) Emergency Departments in the Makkah region of Kingdom of Saudi Arabia	
Publications (reference): None	
Studied Period: (first subject enrolled): 21 August 2018 (last subject completed): 13 August 2019	Phase of Development: Phase 3
Objectives: Primary Objective: To evaluate the efficacy of Ryanodex® for the treatment of exertional heat stroke (EHS), administered as adjunctive treatment to current standard of care (SOC), compared to administration of SOC only.	
Secondary Objective: To evaluate the safety and tolerability of Ryanodex for the treatment of EHS, administered as adjunctive treatment to current SOC.	
Methodology: Study EGL-4104-C-1801 was a Phase 3, multi-center, double-blind, randomized, 2-arm parallel study of Ryanodex for the adjuvant treatment of EHS administered intravenously (IV), to current	

SOC.

Standard of care (SOC) for the treatment of EHS is defined as effective body cooling and supportive measures, which is to be implemented as quickly as available after diagnosis of heat stroke.

Due to the life-threatening nature of EHS, rapid assessment for inclusion into the study and subsequent immediate treatment was to occur.

Number of Subjects (Planned and Analyzed):

Planned: 100 **Analyzed:** 17

Diagnosis and Main Criteria for Inclusion:

Male or non-pregnant female subjects were to be entered into this study if they were diagnosed with known or suspected EHS as evidenced by meeting all of the following criteria at Screening:

- Subjects had a core body temperature obtained rectally of $\geq 40.0^{\circ}\text{C}$ (104.0°F);
- In the judgment of the Investigator, the subject was likely to be at least 18 years of age
- Subject had recent history or suspected recent history (prior 24 hours) of performing intense physical activity (exertional activity)
- The subject had impaired consciousness level as evidenced by a GCS score < 13
- The subject had tachycardia (heart rate ≥ 100 bpm).

Diagnosis and Main Criteria for Exclusion:

Male or non-pregnant female subjects were to be excluded from entering this study if they were diagnosed with known or suspected EHS and met any of the following criteria at Screening:

- The subject was diagnosed with or was suspected to have an acute clinically severe infection, which in the opinion of the Investigator may have increased the subject's risk for participating in the study and/or may have impaired the ability of performing and/or interpreting study assessments.
- The subject had severe hyperthermia secondary to a condition other than heat stroke (e.g., serotonin syndrome, thyrotoxicosis, pheochromocytoma, or brain hemorrhage).
- The subject required endotracheal intubation as a supportive measure prior to, or at the

time of entering the study.
 
• The subject required administration of sedative drugs (e.g. midazolam, ketamine) for the treatment of psychiatric symptoms (e.g. aggressiveness, agitation) prior to, or at the time, of entering the study. NOTE: The use of sedative drugs, such as benzodiazepines, for the treatment of psychiatric symptoms or seizures appearing after the subject had entered the study, was allowed.• There was likelihood of head trauma in the past six (6) months, or other significant cardiovascular, pulmonary, hepatic, endocrine, or renal illness that in the opinion of the Investigator may have increased the subject's risk for participating in the study and/or may have impaired the ability of performing and/or interpreting study assessments.• A female subject had a positive pregnancy test (urine) or evidence of active lactation. NOTE: Pregnancy test may have been waived if female subject was an unmarried Muslim and performing such a test would be in conflict with her religious faith and cultural background, according to the Investigator.• Recent history, suspected recent history (prior 30 days), or current myocardial infarction.• A known history of allergy or hypersensitivity to dantrolene.• A known history of seizure disorders or epilepsy.• Known concomitant or prior use (within the past 2 weeks) of calcium channel blockers.

Test Product, Dose and Mode of Administration, Batch Number:
 
Ryanodex (dantrolene sodium) for injectable suspension; 250 mg/vial to be reconstituted in 5 mL of sterile water for injection (without a bacteriostatic agent) to yield a 50 mg/mL suspension; was to be administered as a rapid IV push of 2.5 mg/kg or 1 mg/kg, as described in the protocol.
 
[REDACTED]

Duration of Treatment: Up to six (6) hours from Screening to End of Study/Early Termination visit

Reference Therapy, Dose and Mode of Administration, Batch Number:
 
Standard of Care (SOC): All subjects in both treatment groups were to receive SOC. Standard of care for the treatment of EHS was defined as effective body cooling and supportive measures.
 
Supportive Measures: All subjects were to receive adequate supportive measures depending on their clinical status
 
Batch Number: Not applicable

CRITERIA FOR EVALUATION
 
Efficacy

Primary Endpoint: Cumulative incidence of subjects achieving a GCS score ≥ 13 at or prior to 90 minutes post-randomization.

Secondary Endpoints:

- Cumulative incidence of subjects who achieve a GCS score ≥ 13 at planned time points;
- Actual values, changes from baseline, and percent changes from baseline in GCS scores over time;
- [REDACTED]

Dantrolene Plasma Concentration Data

Blood sample was to be collected for the purpose of determining the plasma concentration of dantrolene sodium and was only to be used to demonstrate that treatment was administrated as assigned. This assessment was considered as not needed (Protocol Amendment 1; 11 July 2019) for subjects randomized in 2019 because well-established roles and processes exist to accurately document administration of study drug (Ryanodex).

Safety

Safety was assessed using the following parameters:

- Adverse Events;
- Vital Signs (heart rate, blood pressure, respiratory rate, core body temperature);
- Clinical safety laboratory tests (hematology, coagulation parameters, and blood chemistry);
- ECG monitoring;
- Oxygen saturation (measured with pulse oximeter);
- End-tidal CO₂ (ETCO₂)
- Physical exam
- Brief neurological exam
- Use of concomitant medications

Statistical Methods:

A Statistical Analysis Plan (SAP) was finalized prior to database lock. Statistical methods in the SAP were to take precedence over those described in this protocol. All collected study data was to be presented in subject data listings. Statistical analyses was to be performed using SAS® for Windows, version 9.4 or later.

Sample Size:

A total of 100 (50 per treatment group) eligible subjects were planned to be randomized in this study. The nQuery Advisor 6.01 software was to be used for this sample size calculation. The sample size calculation was based on the assumption that 50% of subjects who receive SOC therapy and Ryanodex was to achieve a GCS score ≥ 13 at or prior to 90 minutes post-randomization, compared with only 14.3% of subjects who receive SOC therapy alone. Under the above

assumptions, 50 subjects per treatment group were to be required to meet the Type I error rate of 0.05, 2-sided and over 95% statistical power to detect the difference between treatments; for a total of 100 subjects for the study.

Baseline:

Baseline body temperature was to be the first rectal temperature $\geq 40.0^{\circ}\text{C}$ taken during the Screening Phase. Baseline results for other study assessments were to be the value closest in time to the baseline rectal temperature and prior to randomization. The SAP may specify additional data handling rules.

Analysis Populations:

The safety population was to include all randomized subjects who received any study treatment (SOC only or SOC plus Ryanodex). The safety population was to be used to analyze all safety endpoints using actual treatment received.

The Intent-to-Treat (ITT) population was to include all randomized subjects who received any study treatment and was to be used as the primary efficacy population. Subjects who achieved a GCS total score of ≥ 13 prior to receiving any study treatment were to be excluded from the ITT population.

The Per Protocol population (PP) was to include all ITT subjects who met all inclusion/exclusion criteria, had a baseline and at least 1 post-baseline GCS total score, and had no major protocol deviations that could affect the efficacy assessments.

The ITT and Per Protocol populations were to be analyzed using planned treatment assignments. Classification of subjects with respect to the ITT, PP, and Safety populations was to be conducted prior to the database lock.

Efficacy Analysis:

The primary analyses of the primary and secondary efficacy endpoints were to be conducted on the ITT population. The PP population analyses of primary and secondary endpoints were to be considered supportive. For the primary endpoint, Logit model was to be used to compare proportion of subjects achieving a GCS score ≥ 13 at or prior to 90 minutes post-randomization between treatment groups.

For the secondary endpoints, the data was to be summarized and compared according to the variable type:

- Continuous data summaries was to include:
- Descriptive summary of number of observations, mean, standard deviation, median, and minimum and maximum values.
- Mixed Model Repeated Measures (MMRM) for inferential statistics was to be used if the Normality assumption is met.
- Non-parametric methods were to be used for inferential statistics if the Normality assumption was not met.
- Categorical data summaries was to include:
- Frequency counts and percentages.

- Logit model for inferential statistics
- Time-to-event data summaries was to use:
- Kaplan-Meier (K-M) methods to depict the data and Cox proportional hazards model for inferential statistics.

Safety Analysis:

The Safety Population was to be used for the safety analysis. No modeling or inferential statistics was to be conducted on the safety assessments.

Other:

Demographics, subject disposition, dosing parameters, and prior/ concomitant medications were to be summarized. Other concomitant therapies and medical history were to be listed.

SUMMARY OF RESULTS

Efficacy:

The primary objective of this Phase 3 study was to evaluate the efficacy of Ryanodex for the treatment of EHS when administered as an adjunctive treatment to the current standard of care (SOC), compared to the administration of SOC only. Standard of care, comprised by body cooling and supportive measures, should be considered as an active control. Evaluations of efficacy were made using the Glasgow Coma Scale (GCS) [REDACTED]

The primary endpoint for the study was the cumulative proportion of subjects achieving a GCS \geq 13 at or prior to 90 minutes post randomization. At baseline, subjects in the SOC + Ryanodex group were reported with a median GCS score of 5.0. Subjects in the SOC only group were reported with a median score of 4.5.

At or prior to 90 minutes post randomization, a greater proportion of subjects in the SOC + Ryanodex group were reported with GCS scores \geq 13 than in the SOC only group.

[REDACTED]

[REDACTED]

[REDACTED]

[REDACTED]

Safety:

This study was designed to assess the safety of Ryanodex in the adjuvant setting with standard of care (SOC) therapy on subjects diagnosed with Exertional Heat Stroke (EHS). Subjects were

randomized to receive Ryanodex plus SOC or SOC treatment alone. Safety evaluations were based on the assessment of treatment emergent adverse events (TEAEs), [REDACTED]

A total of 17 subjects were enrolled, nine of which were randomized to the SOC + Ryanodex treatment group. Subjects were to receive an initial dose of Ryanodex of 2.5 mg/kg administered as an IV bolus within [REDACTED] after randomization, in addition to SOC which was initiated [REDACTED] after diagnosis of hyperthermia.. [REDACTED]

A total of four subjects (44.4%, 4/9) received [REDACTED] Ryanodex doses. [REDACTED]

A total of 14 AEs were reported for 12 subjects (70.6%, 12/17) in groups SOC + Ryanodex or SOC only groups. By treatment group, nine AEs were reported for seven subjects (77.8%, 7/9) in the SOC + Ryanodex group and five AEs for five subjects (62.5%, 5/8) in the SOC only group. Based on severity, two severe AEs were reported, one in each treatment group. No AEs were reported that led to death or study treatment interruption or discontinuation.

Based on the MedDRA version 21.0 classification, the most commonly reported system organ classes were metabolism and nutrition disorders (17.6%, 3/17) and nervous system disorders (17.6%, 3/17), followed by gastrointestinal disorders, investigations, and vascular disorders, each reported at an incidence of 11.8% (2/17). The remaining categories were reported in < 10% of subjects. Of the three subjects with AEs in the system organ class of metabolism and nutrition disorders, two subjects (22.2%, 2/9) were in the SOC + Ryanodex treatment group with the remaining subject (12.5%, 1/8) in the SOC only group. All subjects with AEs reported in the category of nervous system disorders were randomized to the SOC only treatment group with three events of seizure (by PT) reported for three subjects (37.5%, 3/8).

Of the two severe AEs, one subject in the SOC + Ryanodex treatment group was reported with the AE of coma scale abnormal (by PT) in the system organ class of investigations. In the SOC only group, one subject was reported with dyspnoea (by PT) in the system organ class of respiratory, thoracic, and mediastinal disorders.

There were three SAEs reported for three subjects (17.6%, 3/17). One subject (11.1%, 1/9) was randomized to the SOC + Ryanodex and two subjects (25.0%, 2/8) to the SOC only group.

In the SOC + Ryanodex, the SAE reported was presented by PT as coma scale abnormal. In the SOC group, the SAEs were reported in each subject by PT as seizure and dyspnoea, respectively.

CONCLUSIONS

Study EGL-4104-1801 was a Phase 3, multicenter, double blind, randomized, 2-arm, parallel, active controlled trial to evaluate the safety and efficacy of Ryanodex as adjuvant treatment to standard of care (SOC), compared to SOC only, in subjects with Exertional Heat Stroke (EHS).

Ryanodex (dantrolene sodium) for injectable suspension was administered as a rapid IV push. Glasgow Coma Scale (GCS) was used to assess subjects' neurologic condition in the study. The primary efficacy endpoint was the cumulative incidence of subjects achieving a GCS score ≥ 13 at or prior to 90 minutes post-randomization.

. A greater proportion of subjects in the SOC + Ryanodex treatment group achieved a GCS score ≥ 13 at or prior to 90 minutes post randomization, compared to the SOC only group. In addition, the cumulative incidence of GCS score ≥ 13 over time was higher in the SOC + Ryanodex group at all planned time points throughout the study.

Date of Report: 6 January 2020

**Document Date: January 3, 2020**

## 9.7 STATISTICAL METHODS PLANNED IN THE PROTOCOL

### 9.7.1 Statistical and Analytical Plans

[REDACTED] lock for the clinical trial protocol EGL-4104-C-1801. Highlights from the statistical analyses proposed for this study are discussed below.

#### 9.7.1.1 General Statistical Considerations

All collected study data was to be presented in subject data listings. Statistical analyses were to be performed using SAS® for Windows, version 9.4 or later. Descriptive statistics (n, mean, standard deviation, median, minimum and maximum) were to be calculated by treatment group for continuous variables. Frequencies and percentages were to be presented by treatment group for categorical variables.

#### 9.7.1.2 Data Convention and Related Definitions

##### 9.7.1.2.1 Baseline Definition

Baseline body temperature was to be the first rectal temperature  $\geq 40.0^{\circ}\text{C}$  taken during the Screening Phase. Baseline results for other study assessments were to be the value closest in time to the baseline rectal temperature and prior to randomization. The SAP may specify additional data handling rules.

##### 9.7.1.2.2 Duplicate Data

For unplanned duplicate data within a protocol-specified time point, the last measured value was to be used for the analysis. If it is not possible to identify the “last measured value”, the average of the duplicate values was to be used.

### **9.7.1.2.3 Outliers**

Data points that appear to be outliers (i.e., clinically identified to be too small or too large) were to be investigated and were not to be excluded from the listings. If the clinician confirms that a data point was truly an outlier and was not clinically possible, two analyses were to be performed, one with the outlier data point and one without it. Any such analysis was to be clearly indicated and footnoted.

### **9.7.1.2.4 Handling of Missing Data**

**Every effort was to be made to obtain required data at each scheduled evaluation from all subjects who have been randomized to minimize missing data. The following methods were to be used to handle missing data for efficacy and safety evaluations.**

#### *9.7.1.2.4.1 Handling of Missing Data for Efficacy Evaluations*

For efficacy data points the following methods were to be used for the post baseline time points with missing assessments:

- If the data point was categorical in nature then the result from the missing data point was to be considered as failure (i.e., non responder) for analysis purposes
- If the missing data point was continuous in nature, then Mixed Model Repeated Measures (MMRM) was to be used to adjust for the missing values
- If the data point was a time-to-event endpoint then the result from the missing data point was to be considered no event and censored based on the last available date/time

#### *9.7.1.2.4.2 Handling of Missing Data for Safety Evaluations*

With respect to summaries of AEs, only AEs that were treatment emergent were to be tabulated. Treatment-emergent AEs were defined as AEs with start date and time  $\geq$  date of randomization.

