### 9.7.1.5.1 Adverse Events

Adverse events were to be coded using the most recent version of Medical Dictionary for Regulatory Activities (MedDRA). Treatment Emergent AE's (TEAE) were defined as events which started on or after the start date and time of randomization, or which worsened after the start date and time of randomization. TEAEs were to be summarized by treatment group, System Organ Class, and preferred term. The following TEAE summaries were to be provided:

- Overall (i.e., regardless of severity or relationship to treatment)
- By severity grade (mild, moderate, or severe)
- By investigators causality assessment (related, possibly related, probably related or unrelated)

In addition, separate summaries of serious adverse events, and adverse events resulting in study discontinuation will be presented.

clinically significant) and Abnormal (clinically significant)) with counts and percentages

A large rectangular area of the page is completely blacked out, indicating the redaction of sensitive data. The redaction is approximately 750 pixels wide and 440 pixels high, starting below the text 'clinically significant) and Abnormal (clinically significant)) with counts and percentages'.

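### The SAP gives two conflicting definitions of a treatment-emergent adverse event, and no visible text says which one produced the AE tables

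*SAP*

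**What the plan says.** Two SAP sections define the same term.

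- **9.7.1.2.4.2, Handling of Missing Data for Safety Evaluations:** "Treatment-emergent AEs were defined as AEs with start date and time" at or after the date of randomization. The onset carries a time but the randomization threshold does not, and worsening is not mentioned. The section also states that "only AEs that were treatment emergent were to be tabulated".
- **9.7.1.5.1, Adverse Events:** treatment-emergent events are "events which started on or after the start date and time of randomization, or which worsened after the start date and time of randomization". The TEAE summaries by treatment group, system organ class and preferred term follow directly from this.

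The protocol synopsis (Statistical Methods) gives the SAP precedence over the protocol, which does not rank one SAP section over another. The safety results in the synopsis are said to rest on TEAEs, and the visible text there does not define the term.

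**The concern.** The definition decides which events enter the TEAE tables, so two programmers working from the same SAP could produce different tables.

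The design makes the disputed cases possible. Every subject enters acutely ill ("The subject had impaired consciousness level as evidenced by a GCS score < 13"). The exertion may lie up to a day back ("recent history or suspected recent history (prior 24 hours) of performing intense physical activity"), so the illness can begin on an earlier calendar date. Participation is short ("Up to six (6) hours from Screening to End of Study/Early Termination visit"), so screening and randomization usually share a calendar day. A threshold on date alone then cannot separate same-day events before randomization from those after it.

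Safety and tolerability is the secondary objective, and the arms have 9 and 8 subjects, so a single reclassification is visible in an incidence.

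**Working it through.** **Step 1. Compare the rules case by case.** The 9.7.1.2.4.2 rule can be read as calendar date (literal) or as date and time (assuming the time was left out by oversight). Would the event count as treatment-emergent?

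| Onset | Worsened after randomization | 9.7.1.2.4.2, calendar date | 9.7.1.2.4.2, date and time | 9.7.1.5.1 |
|---|---|---|---|---|
| Earlier date | No | No | No | No |
| Earlier date | Yes | No | No | **Yes** |
| Same day, before randomization | No | **Yes** | No | No |
| Same day, before randomization | Yes | Yes | **No** | Yes |
| At or after randomization | No | Yes | Yes | Yes |
| At or after randomization | Yes | Yes | Yes | Yes |

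The calendar-date reading conflicts with 9.7.1.5.1 in rows 2 and 3, and the date-and-time reading in rows 2 and 4. Row 2 conflicts under both. Under the calendar-date reading neither rule contains the other: one counts row 3 only, the other row 2 only.

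**Step 2. Reproduce the reported figures** (synopsis, Summary of Results, Safety).

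- SOC + Ryanodex: 9 AEs in 7 subjects; 7/9 = 77.8%.
- SOC only: 5 AEs in 5 subjects; 5/8 = 62.5%.
- Overall: 9 + 5 = 14 AEs in 7 + 5 = 12 subjects; 12/17 = 70.6%.

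All agree with the report.

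**Step 3. How many events are a subject's only event?**

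- SOC only: five events in five subjects means one each, so removing any one event removes a subject from the numerator.
- SOC + Ryanodex: 9 − 7 = 2 extra events. They fall either in one subject (3, 1, 1, 1, 1, 1, 1) or in two (2, 2, 1, 1, 1, 1, 1). So six or five subjects have a single event, and the other three or four events belong to subjects with more than one.

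**Step 4. Effect of reclassifying one subject.** The shift is 1/9 = 11.1 points, 1/8 = 12.5 points, or 1/17 = 5.9 points overall.

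| Change | SOC + Ryanodex | SOC only |
|---|---|---|
| Reported | 7/9 = 77.8% | 5/8 = 62.5% |
| A subject's only event is removed | 6/9 = 66.7% | 4/8 = 50.0% |
| An omitted event is added in a subject with no reported AE | 8/9 = 88.9% | 6/8 = 75.0% |

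Removing one of the three or four non-single events in the SOC + Ryanodex arm leaves 7/9 unchanged.

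The reported difference between arms is 7/9 − 5/8 = 11/72 = 15.3 points. With one subject reclassified in one arm it lies between 7/9 − 6/8 = 2/72 = 2.8 points and 7/9 − 4/8 = 20/72 = 27.8 points.

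For a single preferred term, seizure in SOC only (3/8 = 37.5%) would become 2/8 = 25.0% or 4/8 = 50.0%.

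**The case against.** The best reply is that 9.7.1.5.1 is the dedicated AE section, carries the complete definition and leads straight into the planned summaries, so a programmer would naturally use it. The other text is a two-sentence note under missing data. Because that note asks for an onset time, its threshold probably just lost the words for time. If so, no event is wrongly included, and the scenarios that remove an event fall away.

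This is a fair account of what probably happened, and it may mean that no table changes. It does not remove the conflict. The missing-data note is worded as a general definition, gives no rule for missing onset times, and itself says that only treatment-emergent events are tabulated. Restoring the time still leaves worsening out, so rows 2 and 4 remain in conflict.

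Other points stand as limits on the claim:

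- The SAP text describes itself as highlights, and both it and the safety results are partly redacted. A ruling between the definitions could exist in text that is not visible.
- If worsening was recorded as a new event with its own onset, the two rules agree under the date-and-time reading. The recording convention is not shown.
- An abnormal coma scale was reported as an AE on SOC + Ryanodex although every subject entered with a low GCS. This suggests that deterioration from baseline did reach the tables. It is not proof, since a calendar-date rule could capture the same event.
- Both rules are anchored to randomization in both arms, so no direction of bias is shown.

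**Conclusion.** The concern holds. The two definitions cannot both be followed, and the 9.7.1.2.4.2 version misclassifies some events under either reading. This is an error in the written rule and should be corrected.

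Its demonstrated effect on the reported counts is nil, because onset times are not available. The one-subject shifts of 11.1 and 12.5 points are conditional: they apply only if the 9.7.1.2.4.2 definition was used and a subject falls in one of the disputed rows. They are sizes per reclassified subject and do not cap the total effect.

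The reach is limited. SAP 9.7.1.5 plans no inferential safety analysis, 9.7.1.1 has all data listed by subject, and 9.7.1.5.1 says "separate summaries of serious adverse events, and adverse events resulting in study discontinuation will be presented". The primary endpoint is untouched.

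**What to change.** 1. Replace the definition in SAP 9.7.1.2.4.2 with that of 9.7.1.5.1, or with a cross-reference to it, so that one rule applies throughout: onset at or after the date and time of randomization, or worsening after that date and time.
2. State in the report which definition produced the 14 AEs in 12 subjects.
3. If it was the one in 9.7.1.2.4.2, re-derive the treatment-emergent flag from the date-time stamps, including worsening, and rerun the AE tables.

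The first two steps cost one sentence each in the SAP and the report. The third is needed only if the 9.7.1.2.4.2 definition was used, and it covers 17 subjects.
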